14.6. Pharmacodynamic Analyses

Descriptive statistics (number, mean, median, standard deviation, minimum, and maximum) will be used to summarize LDL-C, TC, HDL-C, non-HDL-C, TGs, apoB, hs-CRP, glucose, [REDACTED], [REDACTED] HbA_{1C}, HOMA-IR, [REDACTED], and 2-hour PPG levels at each assessment by treatment group and to summarize the change from baseline and the percent change from baseline by treatment group at each postbaseline assessment.

The primary and secondary efficacy endpoint will be analyzed using analysis of covariance (ANCOVA), with treatment group as a factor and baseline value as a covariate. The ANCOVA will be performed using the FAS, with subjects included in their randomized treatment group regardless of the treatment they actually received. Subjects who are missing their Week 12 LDL-C will have their Week 12 value imputed by last postbaseline observation carried forward (LOCF). The least squares mean (LSM) and standard error (SE) for percent change estimate will be provided for both treatment groups, along with the PBO-corrected LSM, its 95% confidence interval (CI) and associated p-value. We will analyze observed data and LOCF data separately.

The same analysis will be performed as sensitivity analysis on treatment completer set for primary and secondary efficacy endpoints.

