#### **5.3.1** Analysis for the Efficacy Parameters

For the primary efficacy analysis, percent change in LDL-C at week 12 and the secondary endpoints of percent change in hs-CRP, non-HDL-C, HDL-C, TC, TG, and apoB at week 12 will be analyzed using the analysis of covariance (ANCOVA) method. The ANCOVA model will include treatment as factor, and baseline value as covariate. The model assumptions for ANCOVA will be assessed and if these assumptions are severely violated, alternative non-parametric approach will be performed.

An example SAS code for ANCOVA analysis is shown as below:

PROC MIXED DATA=adeff; class armcd; model pchg = blres armcd / solution ddfm=kenwardroger; ; lsmeans armcd / diff=control ('ref') cl;

The least square mean (LSM) and standard error (SE) for percent change estimate will be provided for all the treatment groups, along with PBO-corrected LSM, its 95% confidence interval (CI) and associated p-value.

For hs-CRP and TG, a non-parametric (Wilcoxon rank-sum test) analysis with Hodges-Lehmann estimates and confidence interval will also be performed because based on historical knowledge, publication precedence (Brendan et al., 2006) and recent data available, hs-CRP and TG are known to be skewed by extreme values and have nonnormal distribution.

Confidential

Page 19 of 38

Version 1.3, July 23, 2019 Statistical Analysis Plan

For other secondary endpoints, number and percent of subjects with LDL-C < 70mg/dL at week 12 will be tabulated by treatment. Number and percent of subjects LDL-C reduction  $\geq$  50% from baseline to Week 12 will be tabulated by treatment. Chi-sq test or fisher exact test will be performed between the FDC-treated arm and EZE-treated arm and PBO-treated arm for those two endpoints. Only observed data will be used, i.e. the denominator will be number of subjects who have LDL-C value at perspective time point. Efficacy data (actual value, change and percent change from baseline) from all visits will be presented using descriptive statistics using both conventional and standard units. A figure of mean (+/- SE) value or median (IQR) as appropriate, over time will be provided for these efficacy parameters.

Efficacy data will also be listed.

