#### 5.3.3 Sensitivity Analysis for Efficacy Endpoints

- A sensitivity analysis for primary and secondary efficacy endpoints will be performed using the ANCOVA model on Treatment Completer Analysis Set.
- The observed case data only (no imputations for missing data) analyses will also be used for sensitivity analyses for primary and secondary endpoints. Observed data analysis will be conducted using FAS.
- By-visit summary for all efficacy endpoints (LDL-C, non-HDL-C, HDL-C, TC, TG, ApoB, hs-CRP) will be provided for both conventional and standard units.

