### **5.4 Exploratory Analyses**

For exploratory endpoints (change and percent change from baseline to Week 12 in HbA1C, fasting glucose,

HOMA-IR index, and 2-hour PPG), the data will be analyzed in the similar fashion as for the primary endpoints. For fasting plasma glucose,

HbA1C, 2-hour PPG and the baseline is the predose Day 1/Week 0 (Visit T1) value. If no value is available at Visit T1, then the last value prior to first dose of IMP will be used as baseline.

Sensitivity analyses will be used to examine if the potential data issues previously identified at 3 sites in Study (Sites ) impact the

Confidential

Page 20 of 38

Version 1.3, July 23, 2019 Statistical Analysis Plan

efficacy results of this study. The sensitivity analysis will repeat selected key analyses including all FAS subjects, as listed below:

- 1. Patient Disposition
- 2. Demographic and Baseline Characteristics Full Analysis Set
- 3. Summary Statistical Analysis of Percent Change from Baseline in Primary Efficacy Endpoints at Week 12 Full Analysis Set
- 4. Summary Statistical Analysis of Percent Change from Baseline in Secondary Efficacy Endpoints at Week 12 Full Analysis Set
- 5. Statistical Analysis of Median Percent Change from Baseline in hs-CRP and TG at Week 12 via Non-parametric Approach (Observed Data) Full Analysis Set
- 6. Statistical Analysis of Percent Change from Baseline in HbA1C Full Analysis Set
- 7. Statistical Analysis of Percent Change from Baseline in Fasting Glucose Full Analysis Set

8.			
9.			

Additional exploratory and sensitivity analyses may be performed as needed.

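### hs-CRP is analysed by ANCOVA of raw percent change although the SAP calls it skewed; the added Wilcoxon test has no baseline adjustment, and neither result is named as the main one

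*SAP*

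**What the plan says.** Percent change in hs-CRP at Week 12 is a secondary endpoint (SAP 3.3), with FDC-PBO, FDC-EZE and EZE-PBO all named as secondary objectives (SAP 3.1). SAP 5.3.1 states that "percent change in hs-CRP, non-HDL-C, HDL-C, TC, TG, and apoB at week 12 will be analyzed using the analysis of covariance (ANCOVA) method". The example code is "model pchg = blres armcd / solution ddfm=kenwardroger", with no log or rank transform on either side.

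For hs-CRP and TG the same section adds that "a non-parametric (Wilcoxon rank-sum test) analysis with Hodges-Lehmann estimates and confidence interval will also be performed", giving as its reason that "hs-CRP and TG are known to be skewed by extreme values and have nonnormal distribution". There is also a general fallback for the ANCOVA: "if these assumptions are severely violated, alternative non-parametric approach will be performed". It has no criterion and names no method.

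The non-parametric analysis has its own entry among the key analyses repeated on the full analysis set (SAP 5.4): "Statistical Analysis of Median Percent Change from Baseline in hs-CRP and TG at Week 12 via Non-parametric Approach (Observed Data) Full Analysis Set". Protocol 14.6 names only ANCOVA for secondary endpoints. Under SAP 5.1 the hs-CRP baseline is a single last value, whereas the basic lipids use the average of S3 and T1. No section ranks the ANCOVA and the Wilcoxon result for hs-CRP.

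**The concern.** Percent change of a right-skewed variable is itself right-skewed, and a few large ratios can dominate the arithmetic mean that ANCOVA compares. With a single-value baseline, one unusual reading enters both the denominator of the percent change and the raw covariate. The planned rank test resists extreme values but gives up the precision that baseline adjustment would bring. If the two tests disagree, the SAP does not say which one answers the secondary objective. At stake are power for FDC-PBO and FDC-EZE, an interpretable effect size, and freedom from choosing between two p-values after the fact.

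**Working it through.** **The plan's own figures.** SAP 4.4 gives 78 × 3 = 234 subjects and ties that number to the co-primary family only. The documents give no hs-CRP standard deviation, correlation, effect or power, so there is no hs-CRP figure to reproduce. Every input below except the planned 234 subjects and the approximate count of 45 sites is an assumption.

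**Inputs.**
- Size: the Efficacy Analysis Set drops 3 sites (SAP 5.2.1.2). With about 45 sites (Protocol 7.7) of average size and no missing data, 234 × 42/45 = 218, or about 73 per arm.
- Baseline: log B = σa.
- Week 12: log W = σ(ρa + √(1−ρ²)e) + log(ratio), with a and e standard normal, σ = 0.9 or 1.1, and ρ = 0.5, 0.65 or 0.8.
- Ratio to placebo: 0.70 for FDC and 0.90 for EZE.
- Percent change = 100(W/B − 1).
- Spike scenario: each visit value is multiplied by 6 with probability 5%.
- Test level: two-sided 0.05, 6,000 simulated trials per setting.

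**FDC-PBO power (%).** Rank ANCOVA means rank of percent change on rank of baseline. Log ANCOVA means log(W/B) on log B. The last column is the share of trials in which the two planned tests disagree on significance.

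| σ, ρ | Planned ANCOVA | Wilcoxon | Log ANCOVA | Rank ANCOVA | Planned tests disagree |
|---|---|---|---|---|---|
| 0.9, 0.5 | 51.9 | 64.1 | 78.8 | 76.3 | 27.5 |
| 0.9, 0.65 | 72.5 | 79.9 | 88.3 | 86.1 | 18.4 |
| 0.9, 0.8 | 94.2 | 96.2 | 98.0 | 97.4 | 4.8 |
| 1.1, 0.5 | 30.9 | 47.4 | 61.4 | 58.7 | 29.5 |
| 1.1, 0.65 | 46.6 | 61.4 | 72.0 | 69.8 | 27.4 |
| 1.1, 0.8 | 78.5 | 84.8 | 90.0 | 88.3 | 13.8 |
| 0.9, 0.5, spikes | 27.8 | 53.8 | 67.4 | 67.1 | 36.7 |
| 0.9, 0.65, spikes | 34.0 | 67.7 | 74.1 | 75.6 | 40.7 |
| 0.9, 0.8, spikes | 43.8 | 85.9 | 83.5 | 90.6 | 44.3 |
| 1.1, 0.5, spikes | 19.9 | 41.2 | 54.3 | 52.2 | 32.0 |
| 1.1, 0.65, spikes | 25.8 | 51.6 | 60.8 | 60.1 | 34.5 |
| 1.1, 0.8, spikes | 36.0 | 72.1 | 73.8 | 77.5 | 41.1 |

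**Gains, by subtraction.** The planned ANCOVA is the weakest of the four in every row. Against it, rank gains 3 to 28 points without spikes (97.4 − 94.2 to 58.7 − 30.9) and 32 to 47 with them. Against Wilcoxon, rank gains +1 to +13 (97.4 − 96.2 to 67.1 − 53.8) and log −2 to +15 (83.5 − 85.9 to 78.8 − 64.1).

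**Other contrasts, planned ANCOVA against log ANCOVA.**
- FDC-EZE: 15-65% against 35-80%; with spikes 9-21% against 31-54%.
- EZE-PBO: 9-24% against 10-22%; with spikes 8-11% against 9-15%. There is no clear gain.

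**Type I error over the 12 settings.** ANCOVA 4.1-5.3%, Wilcoxon 4.5-5.4%, log 4.5-5.5%, rank 4.4-5.3%. The chance that at least one of the two planned tests falls below 0.05 is 7.6-8.5%.

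**Stability, FDC-PBO, σ = 1.1, ρ = 0.65 (5th to 95th percentile of the estimate).**
- LSM difference: −88 to −9 points; with spikes −137 to +17.
- Hodges-Lehmann: −45 to −7; with spikes −46 to −2.
- Log model: −44 to −12%; with spikes −45 to −9%.

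**Different inputs.** With 78 per arm, σ 0.8-1.2, ρ 0.5-0.7 and ratios 0.75 and 0.65, log ANCOVA beat the planned ANCOVA by 2 to 41 points and Wilcoxon by 1 to 15. A true 25% geometric-mean reduction appeared as an LSM difference of −30 to −52 points, depending on σ and ρ.

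**TG (σ = 0.45, ratio 0.85-0.90, ρ 0.5-0.8).** Without spikes, the planned ANCOVA has 33-94% and log 36-95%, a gain of 1 to 7 points. With the same 5% six-fold spikes: ANCOVA 9-18%, Wilcoxon 19-76%, log 19-45%, rank 24-83%.

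**The case against.** A reader might infer that the SAP ignores the skew. It does not. The Wilcoxon and Hodges-Lehmann analysis runs whatever the diagnostics show, so the undefined fallback matters little for hs-CRP, and the Hodges-Lehmann estimate is already nearly as stable as the log model.

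A reader might also infer that ANCOVA is the designated lead. The wording leans that way, since ANCOVA is the stated method and Wilcoxon is an addition, but nothing ranks them. Protocol 14.6 is weak support because the SAP supersedes it. The sentence "A sensitivity analysis for primary and secondary efficacy endpoints will be performed using the ANCOVA model on Treatment Completer Analysis Set" concerns the analysis set and does not choose a lead method.

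Set against the robust test already planned, the power gain is modest and conditional. Adding a log model alone would not end disagreement: log ANCOVA and Wilcoxon still differ in 3-24% of trials without spikes and 10-22% with, and under the null the chance that either is significant is 6.6-8.2%. Naming one deciding analysis is what removes the choice.

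The inputs are all assumed, and log-normality favours the log model. All of this stands, and it limits the size of the point. It does not rescue the raw percent-change ANCOVA, which came last for FDC-PBO in every setting, nor does it supply the missing ranking.

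**Conclusion.** The point holds as a minor one. The planned ANCOVA for hs-CRP does not suit a variable that the SAP itself describes as skewed, the planned robust test forgoes baseline adjustment, and the main result is not designated. The cost is power for FDC-PBO and FDC-EZE, an unstable LSM difference, and an open choice between two tests.

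It would be wrong to infer inflated error in either test or bias in the ANCOVA contrast. Each test is near 5%, and the contrast is valid for a difference in arithmetic-mean percent change; that quantity is simply unstable under skew. The LDL-C co-primaries are untouched, and SAP 4.4 promises nothing for hs-CRP.

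It would also be wrong to infer that TG is exempt because it varies less. That holds only without extreme values. Six-fold TG spikes may be implausible, and averaging two baseline visits would damp them, but the documents give no spike size for either marker.

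The ordering of methods for FDC-PBO rests on log-normal data with or without the assumed spikes. The sizes are illustrative.

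**What to change.** Before unblinding, name one main hs-CRP analysis that is robust and baseline-adjusted, for all three comparisons.

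- **Preferred:** rank ANCOVA, specified as rank of percent change on rank of baseline, reported with the planned Hodges-Lehmann estimate and confidence interval. It keeps the percent-change endpoint of SAP 3.3 and beat both planned tests for FDC-PBO in every setting. The exact form matters: ranking the Week 12 value instead gave 85.0% against 85.9% for Wilcoxon at σ = 0.9, ρ = 0.8 with spikes.
- **Acceptable alternative:** ANCOVA of log(Week 12/baseline) on log baseline, back-transformed with a 95% confidence interval.

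Keep Wilcoxon as the sensitivity analysis, make the raw percent-change LSM for hs-CRP descriptive, drop the undefined fallback for this endpoint, and record the change in SAP 4.6. For TG, at least state which of the two planned analyses is the main one.

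The cost is SAP wording and one model on data already collected. With the rank model, the p-value and the estimate come from different methods and could conflict. With the log model, the effect becomes a geometric-mean rather than an arithmetic-mean percent change, and a rule is needed for any values below the assay limit.

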#### 5.2.1.2 Efficacy Analysis Set

The Efficacy Analysis Set (EAS) is defined as FAS excluding 3 study sites (Sites ). These sites were suspected of good clinical practice (GCP) violation in an earlier phase 3 study and are under investigation. Therefore, to ensure the integrity and quality of the data and related analyses, we will use the Efficacy Analysis Set for the primary efficacy analyses. We will also conduct sensitivity analysis for efficacy analyses using FAS.

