## 5.3 Primary Efficacy Endpoints and Analyses

For all efficacy analyses, the EAS will be used, with patients included in their randomized group, regardless of the treatment they actually received.

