#### 5.3.2 Missing Data Imputation

Missing LDL-C data at week 12 will be imputed using the last post baseline observation carried forward (LOCF).

Observed data and LOCF data will be analyzed separately for primary and secondary efficacy endpoints.

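### The two LDL-C responder endpoints get a p-value but no between-arm difference with a confidence interval, and the <70 mg/dL comparison of FDC with EZE leaves out baseline LDL-C (minor; secondary endpoints only)

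*SAP*

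**What the plan says.** SAP Section 5.3.1 gives the percent-change endpoints an ANCOVA with treatment and baseline value, reported as least squares means with a placebo-corrected difference, 95% CI and p-value. For hs-CRP and triglycerides it adds Hodges-Lehmann estimates with an interval.

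The two responder endpoints get counts and percentages by arm, and then: "Chi-sq test or fisher exact test will be performed between the FDC-treated arm and EZE-treated arm and PBO-treated arm for those two endpoints". No difference, ratio or interval is mentioned, no covariate enters, and the text does not say whether the test is pairwise or across three arms. The missing-data rule for these endpoints follows directly: "Only observed data will be used, i.e. the denominator will be number of subjects who have LDL-C value at perspective time point".

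The neighbouring sections are general. Section 5.3 says "For all efficacy analyses, the EAS will be used". Section 5.3.2 imputes missing Week 12 LDL-C by LOCF and adds "Observed data and LOCF data will be analyzed separately for primary and secondary efficacy endpoints". Section 5.3.3 says "The observed case data only (no imputations for missing data) analyses will also be used for sensitivity analyses for primary and secondary endpoints", and then "Observed data analysis will be conducted using FAS".

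Baseline LDL-C is used elsewhere in the SAP, as the ANCOVA covariate (Section 5.3.1) and as a subgroup factor cut at 160 mg/dL (Section 5.2.5).

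**The concern.** A p-value beside three percentages does not tell the reader how large the FDC-EZE difference is or how well it is known. The same section supplies exactly that for every percent-change endpoint, so the responder endpoints are the odd ones out.

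For LDL-C below 70 mg/dL there is a second point. Whether a subject can reach the target depends heavily on where the subject starts, and an unadjusted comparison ignores this. The SAP states no stratification factor for the randomisation, so a chance difference in baseline between arms passes straight into the percentages. The fall of at least 50% is already relative to baseline, so the point does not carry over to it.

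What is at stake is the reporting and precision of two secondary endpoints. Protocol Section 14.5 rests study success on the two co-primary LDL-C comparisons, which have their own ANCOVA.

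**Working it through.** **Figures in the plan.** The documents give no responder rate, effect size, SD or dropout rate, so there is no responder figure to reproduce. Available inputs are about 78 subjects per arm (SAP Section 4.4), the entry range of 100 to 220 mg/dL at Visit S3 (Protocol Section 8.1) and the 70 mg/dL threshold.

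**Step 1: dependence on baseline, from the documents alone.** Fall needed = 1 - 70/baseline.
- At 100 mg/dL: 1 - 70/100 = 30.0%
- At 140 mg/dL: 1 - 70/140 = 50.0%
- At 160 mg/dL: 1 - 70/160 = 56.2%
- At 220 mg/dL: 1 - 70/220 = 68.2%

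**Step 2: a model, with every input assumed.** Baseline is normal with mean 145 and SD 28, limited to 100-220 (after truncation, mean 147.9 and SD 24.6). Percent change is normal with SD 17. There are 78 subjects per arm, an upper limit because the EAS drops three sites. The analysis baseline averages S3 and T1, so it can fall slightly outside 100-220; this is a minor approximation.

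P(<70 | baseline b) = Φ[(100(70/b - 1) - mean change)/17], averaged over baseline.
- Mean changes of -20, -25, -30, -33 and -38% give about 5, 8, 13, 17 and 24% below 70 mg/dL.
- At -33% the rate is 21.5% for baseline below 160 mg/dL and 5.7% at or above it.
- One standard error of chance baseline imbalance between two arms is 24.6 × √(2/78) = 3.9 mg/dL.

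**Step 3: what an interval would show.** Take an illustrative 13/78 (16.7%) against 4/78 (5.1%). The difference is 11.5 points, with a Newcombe (score-based) 95% CI of 1.6 to 21.8. Percentages and a p-value do not display that width.

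**Step 4: gain from adjustment, FDC versus EZE, <70 mg/dL** (power in %, 6,000 simulated trials per scenario).

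| Mean change FDC, EZE | Chi-square | Firth logistic | Unpenalised logistic |
|---|---|---|---|
| -30, -20 | 42.9 | 43.6 | 47.4 |
| -33, -20 | 67.7 | 70.0 | 72.4 |
| -38, -25 | 78.6 | 81.0 | 82.3 |
| -38, -20 | 94.6 | 95.8 | 96.2 |

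- Firth gain: 0.7, 2.3, 2.4 and 1.2 points. With 70 per arm (-33, -20; 4,000 trials) power goes from 62.4 to 64.4%.
- Variance of the unadjusted risk difference divided by that of the standardised one: 1.06-1.10 unpenalised and 1.08-1.13 Firth, so roughly 6-13% more subjects. Part of the Firth figure is shrinkage. Its bias is 0.0 to -0.3 points, and CI coverage is 94.8-95.6%.
- No true difference, about 5% responders in each arm: rejection is 4.8% for chi-square, 4.1% for Firth and 6.6% for unpenalised logistic. Much of the larger unpenalised power gain should therefore not be trusted when responders are few.

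**Step 5: where adjustment does not help.**
- Fall of at least 50%: variance ratio 0.99-1.00.
- Placebo, assuming zero mean change: rate 0.35%, expected responders 0.0035 × 78 = 0.27, chance of none 0.9965^78 = 0.76. Fisher power for FDC against placebo is already 91% at -30% and 98% at -33%.

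**Step 6: missing data.** Suppose an arm of 78 has 8 missing and 12 of 70 observed responders. Observed: 12/70 = 17.1%. All missing counted as non-response: 12/78 = 15.4%. All missing counted as response: 20/78 = 25.6%. The shift can go either way.

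**The case against.** The strongest reply is that nothing is wrong. The responder objectives (SAP Section 3.1) speak of the effect of each treatment on the percentage of subjects, without the pairwise wording used for the continuous endpoints. Percentages by arm answer that, and the planned test is an addition. Any reader can subtract two percentages and compute an interval from the published counts. Adjustment helps one contrast of one secondary endpoint by a small amount, all from assumed inputs, and it puts a model-based difference beside an unadjusted one.

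Most of this stands, and it is why the point is minor. What remains is that the contrast and the interval method are best fixed before unblinding, and that baseline is already collected and already a covariate in the same section.

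Three stronger readings are tempting, but the documents do not support them.

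- *The unadjusted test is invalid.* It is not. Allocation is randomised 1:1:1, and chi-square rejected 4.8% and 5.1% in the two null scenarios run.
- *The SAP contradicts itself on the main responder percentage.* Section 5.3.2 does lack an exemption for responders. But Section 5.3.1 gives a rule specific to these endpoints, with its own denominator, and a specific rule naturally governs over a general one. Section 5.1 describes 5.3.2 as covering missing lipid efficacy data in general, and 5.3.2 itself plans an observed-data analysis. The observed-case analyses in 5.3.3 are introduced as additional. Section 5.3 makes the EAS the main set, and Section 5.2.1.2 casts the FAS as sensitivity: "We will also conduct sensitivity analysis for efficacy analyses using FAS". The list of FAS repeats in Section 5.4 names no responder analysis in its legible items, so it settles nothing either way.
- *Using observed data only inflates the response rate.* Step 6 shows that the direction is open, and no dropout rate is given. Loss is also limited, since subjects who stop IMP are asked to continue efficacy follow-up (SAP Section 4.2) and final-visit procedures are sought at early withdrawal (Protocol Section 11.8.2).

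The unstated rule for choosing between chi-square and Fisher is likewise a matter of wording.

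**Conclusion.** The point holds as a cheap, minor improvement to two secondary endpoints. The text of Section 5.3.1 establishes that no between-arm difference or interval is planned and that baseline LDL-C is absent from the 70 mg/dL comparison. The documents' own thresholds establish that the fall needed more than doubles across the entry range, from 30% to 68%.

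The size of the benefit rests wholly on the assumed baseline distribution, change SD, mean changes and 78 per arm. On those inputs it is worth roughly 6-13% more subjects in precision, and about 1-2 points of power with Firth, for FDC versus EZE below 70 mg/dL only. Validity, the co-primary analyses and the criterion for study success are untouched.

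**What to change.** In SAP Section 5.3.1:

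1. Name the pairwise contrasts for both responder endpoints.
2. For LDL-C below 70 mg/dL, FDC versus EZE, add a prespecified logistic model on treatment and baseline LDL-C, fitted by a method suited to sparse cells such as Firth penalisation. Report a standardised risk difference with 95% CI, and keep the planned test alongside.
3. For the fall of at least 50%, and for all comparisons with placebo, keep the planned test and add an unadjusted risk difference with a score or exact 95% CI.

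As a clarification only, Sections 5.3.2 and 5.3.3 could state that observed Week 12 LDL-C in the EAS is the main responder analysis and that LOCF and FAS results are sensitivity analyses.

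The cost is SAP wording and slightly more analysis work, with no new data. Firth shrinks the difference slightly (up to about 0.3 points in the scenarios run), and its test is a little conservative when responders are few.
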